The immediate after-effects of conventional tDCS on dual task walking performance are beneficial yet relatively variable across older adults with high baseline dual task costs to gait speed. We extracted data from all older adult participants described in the previous section who had “at-risk” baseline dual task costs to gait speed of $>20\%$ despite no overt disease or illness ($n=20$; 12 women; dual task cost $\mu\pm\sigma=26\pm13\%$; age= 75 ± 6 years). Conventional tDCS targeting the left dlPFC reduced the dual task cost to gait speed in all but one participant, and at the group level, significantly reduced this outcome as compared to sham stimulation ($p=0.002$). While the mean absolute pre-to-post change in dual task cost from pre-to-post tDCS was 12 percentage points, the standard deviation of change was 10 with a range of 35. These data demonstrate that 1) we can recruit older adults with poor dual task performance, 2) conventional tDCS holds promise to improve dual task performance in these vulnerable individuals, and 3) the effects of tDCS, while beneficial, are quite variable across individuals.

The degree to which conventional tDCS is “on-target” correlates with dual task improvements, yet varies across participants. We completed a pilot RCT in which 20 older adults with slow gait and mild-to-moderate executive dysfunction, yet who were without overt disease or illness, were randomized to a 2- week, 10-session conventional tDCS intervention targeting the left dlPFC (NCT02436915).⁵⁶ tDCS, compared to sham, reduced dual task costs to gait speed and postural sway speed, and improved cognition as assessed by the Montreal Cognitive Assessment (MoCA), at a two-week follow-up ($p<0.05$). Twelve participants also completed a baseline structural brain MRI. Six of these were then randomized to tDCS. We used Stimweaver with each MRI to model generated electric fields based upon the electrode placement and flow parameters used for the intervention. The normal component of the electric field (nE) averaged over the left dlPFC varied considerably, and, correlated closely with reduced dual task costs to gait speed at follow-up ($r^2=0.80$, $p<0.05$). In contrast, the nE over the right dlPFC did not correlate with dual task changes (not shown). These data give us confidence that the left dlPFC is an important target for dual task performance, and optimizing tDCS will likely maximize its effectiveness and reduce inter-subject variability.

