Specific Aim: To conduct a “within-subject” cross-over study to determine the acute effects of single sessions of optimized tDCS, conventional tDCS, and sham stimulation on dual task standing and walking in 30 older adults who are free of overt disease yet who present with poor baseline dual task performance.

Hypothesis 1: Across participants, the effect of conventional tDCS on dual task standing and walking performance will significantly correlate with the average of the nE component over the left dlPFC.

Hypothesis 2: Optimized tDCS will induce A) greater improvements on dual task standing and walking performance as compared to conventional tDCS and both sham conditions, and B) these effects will be more consistent across individuals as compared to conventional tDCS.

Study Design

We will conduct a “within-subject,” double-blinded, randomized controlled study comparing the after-effects of single sessions of conventional tDCS, optimized tDCS, and two different sham conditions on dual task performance in men and women aged 65-85 years with poor baseline dual task performance. Participants will have the option to complete a structural and functional brain MRI. They will complete four visits during which they will receive one of the four interventions in random order. Visits will be separated by one week to ensure washout of tDCS effects on brain physiology. Dual tasking will be tested before tDCS, after tDCS and again one hour later.

Study Duration (total)

One year

Study Duration for participants

Up to 8 weeks

Participant Selection

Participants will be recruited from the Boston area community, senior housing facilities in urban and suburban areas, research recruitment repositories including the "Mobility and Brain Function" repository, multiple clinics at the BIDMC, and advertisements within regional media outlets and website posting (IFAR and clinicaltrials.gov).

We aim to obtain complete datasets in 30 participants. We expect to enroll 36 individuals to achieve this aim.

Inclusion criteria

- Men and women aged 65-85 years;
- Poor dual task performance, defined as a preferred gait speed that is >10% slower when walking and simultaneously performing verbalized serial subtractions (i.e., dual tasking), as compared to walking normally (i.e. single tasking).

Exclusion criteria

- Unwillingness to cooperate or participate in the study protocol;
- An inability to walk or stand for 30 continuous seconds without an assistive device;

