Optimized tDCS: This intervention will utilize eight gel electrodes with placement and current parameters optimized to the cohort , with the goal of generating an average nE over the dlPFC of the same size as the one delivered by a conventional montage using sponges in an average subject at 1.5 mA of current (we will use prior data from older adults to define this average target).. The direct current delivered by any one electrode will however never exceed 2.0 mA; the total amount of current from all electrodes will not exceed 4 mA. Each 20- minute session will begin and end with a 60-second ramp up/down of current amplitude to maximize comfort.

Optimized sham: An active sham will be used in which very low-level currents (0.5 mA max) are

transferred between the same electrodes used in the active condition throughout the entire 20-minute session. This intervention will be optimized to deliver currents designed to not significantly influence their cortical tissue, but still mimic the cutaneous sensations induced by tDCS. We have shown that this active sham effectively blinds participants and operators to stimulation condition and does not affect functional outcomes.⁶⁶

Pre/post tDCS assessments: Participants will complete a dual task paradigm before, immediately after, and one hour after tDCS administration. Procedures will follow published recommendations^{6,92,93} that produce excellent test-retest reliability.⁹⁴⁻⁹⁹ We have used this paradigm within our research and laboratory for over ten years. Participants will complete two, 60-second trials in each of six conditions:

- Condition 1: Single task: seated cognitive task (see below for description).
- Condition 2: Single task: standing.
- Condition 3: Single task: walking.
- Condition 4: Dual task: standing with cognitive task.
- Condition 5: Dual task: walking with cognitive task.
- Condition 6: Single task: fast walking

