## **Statistical analysis**

Statistical analyses will be performed using JMP 16 software (SAS Institute, Cary NC).

Significance level will be set to 0.05 for all analyses. Descriptive statistics (i.e., mean, standard deviation (SD)) will be used to summarize demographic characteristics of participants and study outcomes. Shapiro-Wilk tests will be used to examine if the data was normally distributed.

Primary analyses will utilize two-way repeated-measures ANOVAs to examine the effects of tDCS on dual-task cost to standing and sway outcomes. The dependent variable of each model is the primary outcomes of standing (i.e., dual task cost to sway speed and area) and walking (i.e., dual task cost to walking speed). Similar analyses will be applied to the secondary outcomes such as (dual task cost to gait stride time variability, and the walking speed and stride time variability within each condition). Model effects will include stimulation condition (i.e., gel-tDCS, sponge-tDCS, gel-sham and sponge-sham), time (pre-, post-stimulation), and their interaction. Age, sex, and BMI will be included as covariates because each is associated with one or more metrics of standing or walking. Tukey's post-hoc testing will be used to compare factor means of significant models.

A secondary exploratory analysis using one-way ANOVAs to compare the effects of the stimulation conditions on the percent changes of the standing and walking outcomes will be performed. Model effect will be stimulation condition.

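### Hypothesis 1 relates electric field to tDCS response without adjusting for pre-stimulation dual task cost, which may lose power and, if field and cost are related, mislead

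*Protocol*

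**What the plan says.** The Protocol (Study Objectives, Aims and Hypotheses) states Hypothesis 1 as a between-person association: the response to conventional stimulation "will significantly correlate with the average of the nE component over the left dlPFC". It does not say whether the effect is a change in points, a percent change, a sham-corrected change or an adjusted value, and it names no covariate.

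The SAP (Statistical analysis) contains no correlation or regression and does not mention nE. Its primary models are repeated-measures ANOVAs with stimulation condition, "time (pre-, post-stimulation), and their interaction". There the pre-stimulation value is a level of the response, for comparing conditions. The covariates belong to those models: "Age, sex, and BMI will be included as covariates because each is associated with one or more metrics of standing or walking". Pre-stimulation cost is not among them.

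The covariate is nevertheless collected. Under Pre/post tDCS assessments the Protocol says: "Participants will complete a dual task paradigm before, immediately after, and one hour after tDCS administration".

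**The concern.** In the condition comparisons each person is their own control, so stable differences in starting cost largely cancel. Hypothesis 1 compares people with one another on an anatomical trait that is not randomised, and there they do not cancel.

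Starting cost may matter. In the earlier older-adult subset, chosen for a cost above 20% and averaging 26%, the "mean absolute pre-to-post change in dual task cost from pre-to-post tDCS was 12 percentage points". This trial enrols from a lower threshold, "a preferred gait speed that is >10% slower when walking and simultaneously performing verbalized serial subtractions". Someone starting near 10% would have to reverse the cost to show a 12-point fall. If change rises with starting cost, then baseline left out is unexplained variance. If nE is also related to starting cost, part of any nE correlation, in either direction, is due to baseline and not to the field.

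Hypothesis 1 is the trial's dose-response claim. It rests on at most 30 people, and fewer if the optional MRI is declined.

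**Working it through.** **The plan's own figures.** No power or target correlation is given for the 30 complete datasets, so there is none to reproduce. The supporting pilot result does check: r² = 0.80 in six people gives t = √(0.80 × 4 / 0.20) = 4.0 on 4 df, two-sided p = 0.016, consistent with the reported p<0.05. The Fisher-z 95% interval for r is 0.30 to 0.99.

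**Inputs.** From the Protocol (Previous Studies): baseline gait cost SD 13, SD of change 10. From the SAP: "Significance level will be set to 0.05 for all analyses", taken as two-sided. Assumed: post-stimulation SD s of 8 to 15, true r = 0.40, and the nE–baseline correlation g.

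**How much of the change baseline explains.** With reduction = pre − post, corr(reduction, pre) = (13² + 10² − s²) / (2 × 13 × 10) = (269 − s²)/260 = ρ.

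**Power when nE is unrelated to baseline.** Partial r = 0.40/√(1 − ρ²). Fisher-z power uses √(n − 3) unadjusted and √(n − 4) adjusted. At n=30:

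| s | ρ | variance explained | partial r | unadjusted | adjusted |
|---|---|---|---|---|---|
| 15 | 0.17 | 3% | 0.41 | 60% | 59% |
| 13 | 0.385 | 15% | 0.43 | 60% | 66% |
| 10 | 0.65 | 42% | 0.53 | 60% | 85% |
| 8 | 0.79 | 62% | 0.65 | 60% | 98% |

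At n=15 (MRI uptake is not stated), power goes from 31% to 34% (s=13) or 49% (s=10).

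**False positives when nE has no effect but correlates g with baseline.** The spurious correlation is ρ × g. Unadjusted rejection at n=30:

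| s | g=0.2 | g=0.3 | g=0.4 |
|---|---|---|---|
| 15 | 5% | 6% | 6% |
| 13 | 7% | 9% | 13% |
| 10 | 10% | 18% | 28% |
| 8 | 13% | 24% | 40% |

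Under this normal model the adjusted test holds 5%. The error can also run the other way. With a true standardised nE slope of 0.4 and g = −0.3, unadjusted power is 26% (s=13) or 14% (s=10), against 61% or 80% adjusted. With g = +0.3 it is inflated to 78% or 91%, against the same adjusted figures.

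**Simulation, 20,000 trials, n=30.** Underlying cost above 10, mean 22, SD 10; measurement noise SD 4; mean reduction about 10 points, SD 9 to 9.5 (all assumed). Here g is the correlation with underlying cost, which is measured with noise, so false-positive rates fall below the closed form.

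- *Effect proportional to cost* (46% mean reduction; change correlates about 0.60 with baseline). Power rises from 48% to 69%, 55% to 77% or 63% to 84%, depending on the assumed strength of the nE effect. With no nE effect, raw change rejects in 8% to 9% of trials at g=0.2 and 16% to 20% at g=0.4; adjusted, 5% to 6%.
- *Additive effect of similar size* (change correlates 0.17 with baseline). Power is 76% either way, or 85% raw against 84% adjusted. At g=0.4, raw change rejects in 5% and adjusted in 6%.

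**The case against.** The strongest reply is that no stated analysis is being criticised. Hypothesis 1 is a hypothesis, and the SAP has no nE model to be right or wrong. A reader might infer that the plan commits to a simple correlation with raw change; the documents do not say so. This stands, and it makes the missing analysis the larger gap. Baseline adjustment is one element of filling it.

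Second, the SAP's exploratory ANOVAs use percent changes, and Hypothesis 1 might do the same. Under a proportional effect that removes the false-positive problem (4.7% at g=0.4) and recovers part of the power (72%, against 63% raw and 84% adjusted). Under an additive effect, percent change is itself inflated, to about 10% to 11% at g=0.4. Adjustment does acceptably under both.

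Third, the size depends on whether the effect is proportional or additive. The Protocol gives only mean, SD and range of change, which cannot settle it. This stands, and it is why the gain is stated as a range starting at nil.

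Fourth, a reader might infer that starting cost sets a hard ceiling on improvement. It does not: dual task cost is a percent change and can fall below zero. The 10% criterion is applied to a brief screening test, not to the visit-day measurement. Because the earlier subset was selected on cost above 20%, part of its change may be regression to the mean. Adjusting for the same visit's pre-stimulation value also addresses that.

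Fifth, no document links nE to baseline cost. Age is one possible common cause, and the SAP names age as a covariate, but only in the ANOVAs.

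**Conclusion.** The point holds conditionally. Neither document includes pre-stimulation cost in the test of Hypothesis 1, the measurement is already collected, and adjusting for it is the better method. At n=30 and a true r of 0.40, the gain for gait runs from about nil if baseline explains 3% of the variance of change to about 25 points if it explains 42%. At the extreme of 62% the formula gives 38 points. These figures rest on an assumed post-stimulation SD, an assumed r and a normal approximation. No baseline SD is given for sway, so nothing can be computed there.

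A reader might go further and conclude that power is certainly lost, or that a positive result would be a baseline artefact. The documents support neither. The first needs change to depend materially on baseline. The second also needs nE and baseline cost to be correlated, for which no figure exists. With an assumed correlation of 0.2 to 0.4, simulated false-positive rates were roughly 5% to 20% unadjusted and 5% to 6% adjusted. The closed form goes higher only where baseline explains 42% or more of the change.

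The change should be made because it protects against both possibilities at almost no cost. It does not replace MRI uptake: the unadjusted correlation detectable with 80% power rises from about 0.49 at n=30 to 0.67 at n=15.

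**What to change.** Add a Hypothesis 1 analysis to the SAP. Regress post-stimulation dual task cost at the conventional-tDCS visit on mean left-dlPFC nE, with that visit's pre-stimulation cost as covariate, separately for gait speed and sway speed. Report the partial correlation for nE with its confidence interval. Using change as the response in the same model only reverses the sign of the nE coefficient, so this also settles what the effect means. Any sham term enters as an additional covariate, not in place of baseline. Fix this before the outcome data are examined, so that the covariate is not chosen on the result.

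The cost is a few lines of SAP text and one degree of freedom. No new data are needed. If baseline proves nearly unrelated to change, the power loss is negligible: 60% to 59% in the least favourable case above.

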Visit 2 (optional)—Functional and Structural MRI: Baseline MRIs will enable current flow modeling, which considers silent infarcts, white matter hyperintensities (WMHs), and functional connectivity. T1, T2, T2- weighted fluid-attenuated inversion recovery (T2 FLAIR), and resting-state functional scans will be completed on a 3T GE system with a quadrature head coil at the Beth Israel Deaconess Medical Center. Two T1 datasets will be acquired: one with fat-suppression to optimize brain and CSF

segmentation and another one without it to optimize skull and skin segmentation. Field-of-view will encompass all the head with coverage up to C1/2 vertebrae and without head cropping. Silent brain infarcts will be identified as focal lesions appearing hyperintense on T2 and hypo-intense on T2 FLAIR scans. White matter lesions will be identified as periventricular and subcortical regions appearing hyperintense on T2 FLAIR. Lesion diameters/volumes will be calculated using an in-house AFNI and FreeSurfer combination pipeline and the Lesion Segmentation Tool for SPM,89 with manual edits as necessary. All volumes will be normalized as a percentage of the total brain parenchyma volume. Parameters: T1: 362 s, TR/TE=2530/3.32 ms, flip angle=70, 1 mm³ isotropic resolution, matrix= 256X256; T2: 283 s, TR/TE= 3200/284 ms, 1 mm³ isotropic resolution, matrix=256X256; T2 FLAIR: 422 s, TR/TE=6000/388 ms, flip angle=120°, thickness=1.0 mm, 0.49x0.49 mm in-plane resolution, matrix=512X512.

Visit 3-6—Effects of tDCS on dual task performance: These visits will be separated by one week. Each participant will complete each of their assessments at approximately the same time of day. On each visit, participants will randomly receive one of four different 20-minute tDCS interventions. They will complete a dual task paradigm before tDCS and immediately after tDCS.

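### The primary model for this four-visit crossover has no visit term, and the protocol does not say whether condition order is balanced over visits

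*Protocol*

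**What the plan says.** The protocol's Study Design section states: "They will complete four visits during which they will receive one of the four interventions in random order". Under Study Procedures, for Visits 3 to 6, it says that "participants will randomly receive one of four different 20-minute tDCS interventions". Neither place names a sequence set, blocking or any balancing over visits.

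On numbers, Participant Selection says "We aim to obtain complete datasets in 30 participants" and "We expect to enroll 36 individuals to achieve this aim". On spacing, Study Design says "Visits will be separated by one week to ensure washout of tDCS effects on brain physiology". The dual task paradigm is run before, immediately after and one hour after stimulation, which makes 12 assessments over the four visits.

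In the SAP (Statistical analysis), the primary repeated-measures ANOVA is specified as: "Model effects will include stimulation condition (i.e., gel-tDCS, sponge-tDCS, gel-sham and sponge-sham), time (pre-, post-stimulation), and their interaction". Age, sex and BMI are the only covariates. The exploratory one-way ANOVA of percent changes has condition as its only effect. Visit, sequence and carry-over terms appear nowhere.

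**The concern.** In a crossover, visit number is a known source of variation, because people get better at a repeated task, tire of it or settle into it. It is normally handled by balancing conditions over visits, by a period term in the model, or by both. Here the documents describe neither. Age, sex and BMI are in effect constant within a person over four weeks, so they cannot absorb a visit effect.

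If order is unrestricted and only about 30 people finish, some conditions will by chance fall at later visits more often than others. Any visit-related change in response then becomes part of the condition contrast in the one trial that is run, and also inflates the residual. The precision of the comparisons between optimized tDCS, conventional tDCS and the two shams is at stake.

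**Working it through.** **Inputs from the documents.** Four conditions over four visits; 30 completers; SD of the pre-to-post change in dual task cost to gait speed 10 percentage points and mean change 12 (protocol, Previous Studies, 20 older adults, conventional tDCS). The documents give no power or balance figure to reproduce.

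**Assumptions.** Order is an independent random permutation for each person. The pre-to-post change drifts linearly by *b* points per visit, with *b* from 0 to 4. The within-person correlation of changes, ρ, lies between 0 and 0.5. The SD of 10 applies to all conditions. Tests are two-sided at 0.05.

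**1. Imbalance under unrestricted order.** Each condition is expected at each visit in 30/4 = 7.5 people, with SD √(30 × 0.25 × 0.75) = 2.37, so the 95% range is 3 to 12 people. For two conditions in one person, the difference in visit number has variance 2 × 1.25 + 2 × 1.25/3 = 3.33. The gap in mean visit number over 30 people therefore has SD √(3.33/30) = 0.33, and 95% of gaps are at or below 0.67. Simulation of 40,000 trials agreed. The fullest and emptiest of the 16 condition-by-visit cells differed by 6 or more people in 91% of trials.

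**2. What cancels and what does not.** Write pre = μ + p(v), and post = μ + p(v) + τ(c) + g(v), where p is practice common to both tests at visit v, g is the visit's shift in the within-session gain, and τ is the condition effect. The change is τ(c) + g(v), so p(v) drops out. With g(v) = *b*·v, the chance error in a contrast of two conditions has mean zero and SD *b*/3. A condition main effect averages pre and post, and so keeps p(v) + g(v)/2.

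**3. Size against the standard error.** SE = 10 × √(2(1 − ρ)/30), which is 2.58 at ρ = 0 and 1.83 at ρ = 0.5.

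| *b* (assumed, points per visit) | SD of chance error | % of SE 2.58 | % of SE 1.83 |
|---|---|---|---|
| 0 | 0 | 0 | 0 |
| 0.5 | 0.17 | 6 | 9 |
| 1 | 0.33 | 13 | 18 |
| 2 | 0.67 | 26 | 37 |
| 4 | 1.33 | 52 | 73 |

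**4. Error rate and precision.** In simulation of the changes (ρ = 0.3, unrestricted order, no visit adjustment), type I error stayed between 4.4% and 5.5% for *b* from 0 to 4. At *b* = 4 the SD of the contrast was 2.58 unadjusted and 2.22 adjusted for visit, a variance ratio of (2.22/2.58)² = 0.74.

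**5. Which term is needed.** A visit main effect enters pre and post alike, so it is subtracted out just as p(v) is. A direct fit confirmed that adding it alone leaves the condition-by-time estimates unchanged to rounding error. Visit-by-time carries g(v), and is the counterpart of a visit term in a model of changes.

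**6. Cost if there is no drift.** Under unrestricted order with 30 people, adjusting for visit multiplies the contrast variance by 1.036 on average. Ignoring the small loss of degrees of freedom, gain and cost break even when *b*²/9 = 0.036 × SE². That gives *b* = √(9 × 0.036 × 3.33) = 1.0 at SE 1.83, and √(9 × 0.036 × 6.67) = 1.5 at SE 2.58.

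**7. Percent change.** A shift common to pre and post does not cancel from a ratio. A 12-point change from the prior cohort's mean cost of 26 is 12/26 = 46%. If practice lowered both values by an assumed 4 points, the same change would be 12/22 = 55%.

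**The case against.** The strongest reply is that the design already guards against ordinary practice. Every visit has its own pre-stimulation test, and the key term is condition-by-time. The protocol also says that the subtraction task is little affected by learning once people know it, uses random starting numbers and random trial order, and lists a familiarization form. Most of this stands: common practice does cancel, and the remaining error averages zero over randomizations. Three limits remain. The protocol puts no size on learning, and the source it cites is, by its title, a reliability study of stride time variability, whereas the primary outcomes are costs to gait speed and sway. The SAP applies Tukey tests to factor means, and condition main effects lack the pre-test protection. The percent-change analysis is not protected either.

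A reader might infer that the trial chose simple randomization over a Williams design. The documents do not show that. Random order is equally compatible with random allocation to balanced sequences; the scheme is unspecified. A four-sequence Williams square is also not clearly better here. Gel and sponge electrodes look different, and under two of the three ways of labelling such a square the gel/sponge pattern is unique to each sequence. Staff who knew the list could then tell active from sham by the second visit. Under all 24 orders, each pattern fits four sequences.

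Carry-over is a weak ground for the point: the protocol's background puts excitability effects at up to 4 hours, against a one-week gap.

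**Conclusion.** The point holds as a modest gap in the analysis model and in the description of the design. The documents do not say whether order is balanced, and the SAP has no term to adjust for visit. If order is unrestricted, chance imbalance over visits is nearly certain with 30 completers, but its consequence depends on an assumed drift in the within-session gain. The added error is 6% to 18% of the contrast SE for 0.5 to 1 point per visit, 26% to 37% at 2 points, and nil without drift. Four points per visit would be 12 points from the first to the last visit, as large as the mean conventional tDCS effect in the prior data, so that row is an extreme.

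A reader might conclude that practice effects bias the comparison of conditions. The check does not support this: the error has mean zero and type I error stays near 5%. What is lost is precision, together with protection for condition main effects and percent changes. The figures also rest on an SD of 10 in every condition and on ρ between 0 and 0.5.

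**What to change.** Add visit (categorical, four levels) and visit-by-time to the primary repeated-measures model, and visit to the exploratory one-way model of percent change. Visit alone is not enough, because it leaves condition-by-time unchanged. The cost is 3 degrees of freedom per added term, and about 4% of contrast variance if there is no drift. Below roughly 1 to 1.5 points of drift per visit the adjustment slightly costs precision; above that it gains. No extra visits or participants are needed, and it can be done even if recruitment is complete.

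State in the protocol how the order is generated. If sequences are already balanced, one sentence settles that part. If the list is not yet fixed, balance conditions over visits in a way that does not let the visible gel/sponge pattern reveal the sequence. A four-sequence Williams square (36/4 = 9 people per sequence) is one option, not a requirement. Balance does not replace the model terms: with Williams sequences split 8/8/7/7 and an assumed drift of 4 points per visit, the simulated test of changes had a type I error of 1.9% without visit adjustment and 5.4% with it.
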